## 2) Significance

Early infant growth patterns and eating behaviors have been related to life-long increases in obesity-risk. However, effective interventions for preventing excess weight gain in infancy are lacking. Additionally, there are currently no empirically-derived recommendations around the critical infant dietary milestone of introduction of solid foods. This is significant given that timing and manner of introduction of solid foods has potential implications for later obesity-risk throughout childhood, adolescence, and adulthood. If the designed prevention program is effective, it will reduce early obesity-risk, improve development of infant satiety cues, and increase infant preference for food variety. Given obesity is related to poor long-term health and psychosocial outcomes, financial burden, and reduced quality of life, an early life obesity prevention program could have significant impact across multiple domains.

### c. FUNDING

#### 1) Sponsor's name and type

This study will be funded using the PI's UC start-up funding and funding from UC's University Research Council (an internal faculty grant).

#### 2) Sponsor's role

The study was developed without input of a sponsor. Study results will also be analyzed, interpreted, and disseminated without input of a sponsor.

#### 3) Location of funds

Funds will be held at UC's Psychology Department.

#### 4) Status of funding

Funding has been approved.

### d. FACILITIES

Baseline and post-treatment study visits to collect outcomes measures will occur at the Schubert Research Clinic (SRC) located in the T-building at Cincinnati Children's Hospital

Medical Center (CCHMC). Intervention sessions will occur at the PI's research lab (the Healthy Kids Lab) located in the Edwards Center on UC Main Campus. We have been approved for access to these facilities.

e. DURATION OF STUDY

The research project will take 12 months to complete.

**Timeline**

	Grant Mos: 1-2	Grant Mos: 3-4	Grant Mos: 5-6	Grant Mos: 7- 8	Grant Mos: 9-10	Grant Mos: 11-12
Recruitment (at child age 2-3 mos)						
Initial Study Visit (at child age 3 mos)						
Treatment Session 1 (at child age 4 mos)						
Treatment Session 2 (at child age 6 mos)						
Treatment Session 3 (at child age 9 mos)						
Final Study Visit (at child age 9 mos)						

Abbreviations: mos = months

f. RESEARCH TEAM

1) Research team and time commitment

Job Title / Responsibility	Time Commitment
PI	10 hr/per wk
Lead Undergraduate Research Coordinator	10 hr/per wk
Graduate Student Interventionists	10/hr per wk
Expert Consultants	< 5/hr per wk

2) Training team members in research ethics

All study team members have complete and up-to-date CITI training.

3) Training team members in research activities

(a) Training

The lead research coordinator and study interventionists will receive direct supervision from the study PI on study recruitment, the study intervention, and study data collection procedures. The lead research coordinator, study interventionists, and study PI will meet weekly for supervision.

(b) Verification

The study PI will verify appropriate use of IRB-approved forms and study procedures during weekly supervision with team members.

**2. PARTICIPANTS:**

a. RECRUITMENT

Participants will be recruited at 2-3 months of age through Pediatric Associates, PSC, a pediatrician practice that has 3 locations in northern Kentucky. If adequate enrollment cannot be achieved through Pediatric Associates, an amendment will be submitted to expand recruitment

to include daycares, Sona system (i.e., student participants can enroll if they have a child meeting study inclusion criteria), and internet and social media sites for our research lab (i.e., The Healthy Kids Lab).

1) Number of participants

The study will enroll 40 total participants. Twenty participants will be randomized to receive the study treatment and 20 participants will be randomized to the control group.

(b) Rationale

This number of participants was determined based on the number of participants feasible to enroll as part of a pilot study while still generating enough data regarding treatment feasibility.

2) Inclusion and exclusion criteria

Participants will be infants aged 3-9 months and their families ( $n = 40$ ). Infants with both normal and elevated weight-for-length will be enrolled. Inclusion criteria include 1) infant has not previously been introduced to complementary foods (i.e., any food besides formula or breastmilk), 2) infant does not have a known developmental delay, 3) infant does not have impaired fine or gross motor skills (which would impact ability for self-feeding), 4) infant does not have a condition currently impacting their feeding and eating, 5) infant born at  $\geq 38$  weeks gestation, 6) infant current weight-for-length  $\geq 10^{\text{th}}$  percentile (Infants with suboptimal growth will be excluded due to potential safety implications of modifying eating and feeding styles of infants with growth difficulties), and 7) parent is a fluent English speaker (because this is the language the intervention will be delivered in).

3) Vulnerable participants

(a) Vulnerability

All study participants will be children less than 1 year old.

(b) Rationale

The objective of the current study is to test an intervention for healthy infant feeding. Therefore, all participants are required to be infants.

(c) Confirmation

A trained research assistant or study PI will complete the informed consent process with a parent/legal guardian of each participant. During that process, the research assistant will confirm that the legal guardian is 18 years of age or older by asking parents to self-report age if they are a young adult believed to be close to 18 years of age. During the consent process, they will also inform the study PI if they have any concerns about a participant's cognitive ability to consent.

4) Risks and discomforts from participating

(a) Type and level of risk or discomfort

Risk or Discomfort	Level
Parental emotional discomfort (anxiety, nervousness) related to introducing their children to solid foods.	minimal
Child risk for choking during introduction of solid foods.	minimal

However, prior research has demonstrated that infant self-feedings are not associated with increased risk of choking (Fangupo et al., 2016).	
Child risk for growth faltering. However, prior research has demonstrated that children introduced to solid foods incorporating self-feeding are not at increased risk for growth faltering in comparison to other children (Townsend & Pitchford, 2012).	minimal

(b) Safety monitoring plan

Despite no greater than minimal risk to participants, we will still actively assess for adverse events related to growth faltering and choking. At each intervention session or study visit, study participants will report on if there were any choking episodes since the last meeting. Additionally, child weight will be measured, with any child failing to gain weight since the last session defined as an adverse event. Between sessions or meetings, parents will be advised to call 911 immediately if their child experiences a choking episode. Participants will also be informed to contact the study PI if there is any concern regarding their child's weight gain or after a choking episode occurs. Any reports of choking episodes provided either at study visits or between study visits will be recorded on the Choking Incident Form. All reported adverse events will be assessed by the study PI.

(c) Reporting

Research assistants collecting adverse event information at study visits and intervention sessions will report this information directly to the PI. Between visits and sessions, study participants will be asked to communicate to the study PI directly if they have any concerns about study participation or if their child experiences an adverse event.

(2) Notification of IRB

Serious adverse events will be reported to the IRB immediately. Other adverse events will be reported to the IRB during the study renewal period.

(3) Other notification

Although not expected, if in the unlikely event we deem participation in the intervention group to be associated with increased risk for choking or growth faltering, study participants will be made aware of this increased risk immediately.

(4) Available resources

During the consent visit, all study participants will receive safety information regarding choking and growth faltering. Study participants will also be referred to talk with their child's pediatrician if they have any concerns.

5) Direct benefits to the participant

Study participants randomized to the intervention group will receive psychoeducation and practice in treatment sessions regarding introduction of complementary foods to

their child. Study participants randomized to the control group will have no direct benefit. Given initial introduction of solid foods occurs only at one time point, a wait-list control design would be inappropriate for the current study.

6) Recruitment activities

(a) Recruitment materials

List: Study Flyer

Pediatrician Recruitment Letter

(b) Personnel

The study PI, lead research coordinator, graduate student interventionists, and expert consultants will be involved in recruitment.

(c) Recruitment activities

We will use opt-in recruitment strategies across all patients at Pediatric Associates, including having handouts for providers to give to patients, having study posters hung at the office, and posting about the study on the practice's social media and in newsletters. Physicians will then be given the option to also have an opt-out recruitment strategy used with the patients for which they are the primary medical provider. Physicians will be approached about using the opt-out strategy by [name], a physician at the practice who is also a collaborator on this research project. The opt-out recruitment strategy will identify children via a systematic chart review by research personnel and practice staff using a procedure from our previous research study (CCHMC 2016-1712). The pediatrician practice has a HIPAA Compliance Officer. In accordance with HIPAA policy, a waiver for review of the information in the primary care office charts and database will be placed on file with this officer. This waiver is between the pediatrician practice and researchers. A file will be kept for patients whose records were reviewed of the study personnel's access to their medical record for purposes of inviting participation into the study protocol. This procedure is consistent with HIPAA legislation (Subpart E Section 164.513, 45 CFR 164.512). A copy of the HIPAA waiver form has been uploaded to the IRB Smartform. For families of children meeting the inclusion and exclusion criteria based upon information in the chart review, the research personnel will create a recruitment letter for each identified child's pediatrician to review and sign inviting the child's guardians to learn more and participate in a screening for the study. Letters will only be sent until our enrollment target is met (n = 40). Enclosed with the recruitment letter, families will receive a flyer describing the study and a return addressed, stamped "do not contact" postcard that a family can mail requesting not to be contacted. All families for whom a postcard is not received within 10 days of mailing will be contacted by phone by the study personnel to explain more about the study, assess the family's interest in participation in the study, and schedule an initial study visit if the family would like to participate. No patient data will be removed from the pediatrician office on children for whom a chart review was conducted or those whose families were sent letters, until 10 days after the mailing. Ten days after mailing, the names, chart review screening forms, and contact information of families who received a recruitment letter and did not return a "do not contact" postcard will be brought to [name] lab at UC. These families will be called by study personnel to explain the study, conduct initial screening, and invite participation. All of these procedures are consistent with the recruitment procedures in our other study (CCHMC 2016-1712).

(d) Participant response

Study flyers will include the PI's contact information.

b. CONSENT PROCESS

1) Presenting information to potential participants

The informed consent process will occur individually with families at their first study visit. It will occur first thing in the visit before any study procedures. A trained research assistant or the PI will review the consent form with the parent participating with the infant and answer parent questions regarding the research study. The parent will be given adequate time to determine whether they would like to participate in the study and will than provide consent if they choose to participate on the informed consent document. Information will be presented in a manner that is understandable to the family.

2) Answering questions from potential participants

Participants will complete the informed consent process one-on-one and in-person with research staff, allowing them the opportunity to ask questions. Families will also be provided contact information for the study PI should they have questions after their initial visit.

3) Indicating consent

Participants will sign an informed consent document to indicate their consent.

4) Legally authorized representative (LAR) for minors or cognitively impaired participants  
Not applicable.

5) Verification of LAR for cognitively impaired participants

Not applicable

6) Avoiding coercion

The research assistant or PI conducting the informed consent process will be someone who has no authority over participants. Participants will be informed that their choice to participate will have no influence on their ability to receive services at Pediatric Associates.

7) Recruitment incentives

All study participants will receive \$50 in gift cards for completion of the first study visit and \$50 in gift cards for completion of the final study visit. Participants will be given the portion of the incentive earned at the end of each completed visit (i.e., \$50 at the end of the first study visit, \$50 at the end of the final visit).

c. CONSENT DOCUMENTS (ICDs)

List: Informed Consent Document

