**Aim 2: Test the impact of the HSF intervention on growth trajectories, appetite regulation, and diet at post-treatment.**

H1: Infants receiving the intervention will experience lower incidence of high weight-for-length ( $\geq 85^{\text{th}}$  percentile) compared to infants in the control condition.

H2: Infants in the treatment condition will show greater satiety responsiveness and lower food responsiveness as assessed through a well-validated parent-report measure (*Baby Eating Behavior Questionnaire* (Llewellyn, van Jaarsveld, Johnson, Carnell, & Wardle, 2010)).

H3: Infants in the treatment condition will consume a greater variety of fruits and vegetables than infants in the control condition as assessed through a food frequency questionnaire completed by parents.

b. **BACKGROUND**

1) Prior research

Pediatric obesity occurs at epidemic rates (Ogden, Carroll, Kit, & Flegal, 2014) with significant health, financial, and psychosocial consequences (Weiss & Kaufman, 2008; Williams, Wake, Hesketh, Maher, & Waters, 2005; Griffiths, Parsons, & Hill, 2010; Freedman, 2007). While many treatments for pediatric obesity exist, obesity remains intractable for many children, and most children participating in treatments do not exhibit clinically meaningful reductions in Body Mass Index. Therefore, prevention of obesity is critical, including prevention efforts within the first year of life. Children with severe obesity begin to deviate in their growth trajectories at as early as 4 months of age (Smego et al., 2017). Infants with high weight-for-length have up to a 9 times greater risk of obesity later throughout the lifespan, even until 60-70 years of age (Baird et al., 2005; Eriksson, Forsen, Osmond, & Barker, 2003). However, effective prevention programs targeting children  $< 2$  years are limited (Blake-Lamb et al., 2016).

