Study participants will be assigned to either the control or treatment condition at their first study visit following completion of informed consent and baseline measures. A computer-generated random number list will be used to determine condition assignment for each participant. Participants will be notified immediately at the study visit of their study condition.

(b) Activities and duration

The first study appointment will occur when the infant is 3 months of age (defined as 3 months 0 days – 3 months 30 days) at the Schubert Research Clinic (SRC) at CCHMC. The infant and at least one parent will attend the appointment. The appointment will begin with completion of the informed consent process with the study PI or trained research assistant. Next, participants will

complete study measures, including infant anthropometrics and parent-report measures of demographics, parental feeding practices and beliefs, and infant appetite. Families will also receive information about how to intervene if their child experiences a choking incident while introducing complementary foods. Following completion of study measures, families will be randomized to either the control or treatment condition using a computer-generated random number list. Participants will receive \$50 for completion of this visit. Participants in the intervention condition will be instructed to not introduce their child to complementary foods prior to their first Treatment Session at 4 months of age. All families will receive safety information regarding monitoring infant growth and choking.

Participants assigned to the treatment condition will attend 3 intervention sessions at the Healthy Kids Lab, located in the Edwards Center on UC campus. The sessions will be scheduled with individual families when the child is 4 months (+/- 30 days), 6 months (+/- 30 days), and 9 months (+/- 30 days) of age. An attendance log of whether participants attend treatment will be kept.

All participants will also complete a final study visit at the SRC at CCHMC when the child is 9 months (+/- 30 days) of age. They will complete a final study visit to complete post-treatment period measurements, which will include infant anthropometrics and parent-report of infant appetite, infant diet, and parental feeding practices and beliefs. Families receiving the intervention will also complete a measure of treatment satisfaction. Participants will receive \$50 for completion of this visit.

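### Baseline weight-for-length is measured before allocation but is used neither in the assignment list nor in the growth ANOVA, so a chance imbalance would be seen but not corrected

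*Protocol*

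**What the plan says.** **Who is enrolled.** Protocol section 2.a.2 (inclusion and exclusion criteria): "Infants with both normal and elevated weight-for-length will be enrolled". There is a floor at the 10th percentile ("Infants with suboptimal growth will be excluded due to potential safety implications") and no ceiling. The expected proportion of elevated infants is not given.

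**How many.** Protocol section 2.a.1: "The study will enroll 40 total participants", and "Twenty participants will be randomized to receive the study treatment and 20 participants will be randomized to the control group". The number was "determined based on the number of participants feasible to enroll as part of a pilot study"; there is no power calculation.

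**How they are assigned.** Protocol section 3.c.3(a): "A computer-generated random number list will be used to determine condition assignment for each participant". Assignment takes place at the first visit, "following completion of informed consent and baseline measures", and section 3.c.3(b) lists infant anthropometrics among those measures. Neither document mentions strata, blocks or minimisation.

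**What is hypothesised and analysed.** Aim 2, H1 expects "lower incidence of high weight-for-length" in the intervention arm, with high meaning at or above the 85th percentile. Protocol section 4 and the SAP's Primary Aim paragraph plan to look at baseline differences, weight-for-length included, as a check on randomisation. They then compare outcomes by ANOVA and name no covariate. The protocol adds a repeated measures model, to be considered only if data are missing. The SAP does not carry that model over.

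**The concern.** Weight-for-length at 3 months is the baseline value of the growth outcome itself. Some infants can already lie above the H1 cut-off when they enter. With 20 per arm, chance can put noticeably more of them in one arm, and part of that difference will persist to 9 months.

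Two tools could deal with this: balance at allocation, or adjustment in the analysis. The value needed for either is in hand before the assignment is drawn, yet the plan uses neither. The baseline check has no stated consequence, so a reader who saw a 6:1 split of elevated infants would be left with an unadjusted growth result that is hard to interpret. The SAP calls this comparison part of the Primary Aim, which raises the stakes somewhat for a pilot.

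**Working it through.** **Inputs from the documents:** 40 infants, 20 per arm; entry at or above the 10th percentile; H1 cut-off at the 85th percentile; ANOVA without covariates. The sample size rests on feasibility, so there is no planning figure to reproduce.

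**Assumptions, not in the documents:** entry weight-for-length follows the growth reference cut at the 10th percentile, so the elevated share is p = 15/90 = 16.7% (range 15% to 30%), about 7 of 40; correlation between 3 and 9 months r = 0.3 to 0.7; two-sided 5% level.

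**1. Chance of imbalance, number of elevated infants left random.** Two independent Binomial(20, p) counts:

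| p | gap of 3 or more | gap of 4 or more |
|---|---|---|
| 15% | 26% | 12% |
| 16.7% | 28% | 13% |
| 20% | 32% | 16% |
| 30% | 39% | 23% |

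**2. The same with the number elevated fixed at K.** Hypergeometric(40, K, 20). For K = 6, 7, 8, 10 and 12, a gap of 4 or more has probability 18%, 9%, 24%, 27% and 30%. The dip at K = 7 is parity: an odd total allows only odd gaps. With K = 7, a 5:2 split or worse has probability 41% and a 6:1 split or worse 9%.

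**3. Effect on the H1 share with no treatment effect.** Bivariate normal, truncated at the 10th percentile at entry. Four infants out of 20 is a 20-point baseline gap, so shift = 0.20 × (rate if elevated at entry − rate if not):

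| r | rate if elevated | rate if not | shift |
|---|---|---|---|
| 0.3 | 27.7% | 13.8% | 2.8 points |
| 0.5 | 38.5% | 12.1% | 5.3 points |
| 0.7 | 52.1% | 9.6% | 8.5 points |

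For scale, the standard error of a 20 versus 20 difference at 16.7% is √(2 × 0.167 × 0.833 / 20) = 11.8 points.

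**4. Continuous score.** The standard error of the baseline difference is √(2/20) = 0.32 SD, and P(|difference| > 0.5 SD) = 11%. A 0.5 SD imbalance moves the unadjusted final difference by r × 0.5 = 0.15 to 0.35 SD. Given that imbalance, the unadjusted test's type I error is 6.5% to 11.6% instead of 5%.

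**5. What adjustment gains.** Using the baseline score multiplies the residual SD by √(1 − r²). For a true 0.5 SD effect, power rises from 35% to 38%, 45% and 60% at r = 0.3, 0.5 and 0.7. Once the covariate is in the model, the remaining precision lost by not stratifying is about 1/(40 − 4) = 1/36 = 2.8%.

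**6. What stratified blocks gain.** With one list per stratum and blocks of 4 (illustrative), the arms can differ by at most 2 elevated infants, so a gap of 3 or more cannot occur. Arm totals can differ by up to 4, that is 18/22.

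**The case against.** The strongest reply is that unstratified 1:1 randomisation of 40 infants is a valid design for a feasibility pilot. That stands. A reader might infer that the growth comparison is biased or its test invalid. The documents do not support this: chance imbalance is already allowed for in the test's unconditional error rate, and even the 8.5-point shift is below one standard error (11.8 points).

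A second reply is that allocation is the wrong place to look. The planned analysis is ANOVA on scores, and for a mean with a baseline covariate, stratifying adds only about 3%. This also stands, and it is why the missing baseline term comes first here and the lists second.

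Third, a 4-infant gap could be read as the typical case. It is not: it cannot occur with exactly 7 elevated infants, and it averages about 13% at 16.7% prevalence. A gap of 3 is the more realistic worry.

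Fourth, H1 speaks of incidence. If that means new cases only, infants already elevated at entry are not at risk, and the carry-over in step 3 would not apply in that form. The documents do not say which is meant; the mean-score argument is unaffected.

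Finally, the absence of strata is inferred from silence in a short protocol. If strata exist, one sentence would settle that part. The ANOVA would still lack a baseline term.

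**Conclusion.** The point holds as a gap in precision and interpretability. Baseline weight-for-length is available before assignment, but the plan uses it only to look for differences. At an assumed 16.7% prevalence and a 20/20 split, a gap of 3 or more elevated infants has about a 28% chance and a gap of 4 or more about 13%. The latter would shift the 9-month share by about 3 to 8.5 points under an assumed correlation of 0.3 to 0.7, reading H1 as the share elevated at 9 months. Prevalence and correlation are assumptions, and the size of the problem moves with them. The documents do not support calling the randomisation faulty or the trial biased. They do support saying that an imbalance, if it arose, would stay in the growth result.

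**What to change.** **Main change (Protocol section 4 and the SAP's Primary Aim paragraph).** State in advance that the growth comparisons include baseline weight-for-length whatever the baseline check shows: the continuous baseline score in the comparison of means, and the stratum (below, or at or above, the 85th percentile at the 3-month visit) in the comparison of the H1 share. With about 7 cases expected, keep the latter simple, for example a Mantel-Haenszel risk difference over the two strata. The data are already collected, so the cost is a few words.

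**Cheap addition (Protocol section 3.c.3).** Prepare two concealed, blocked lists, one per stratum, and read the percentile from the baseline measurements before taking the next assignment. State the target in section 2.a.1 as about 20 per arm, since unfinished blocks may leave a split such as 18/22 with blocks of 4. Because families learn their condition at once, block sizes should vary and stay concealed; larger blocks would allow somewhat larger gaps. The cost is a second list and a percentile look-up, with no extra infants, visits or staff.
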